6.6. Subject Identification and Confidentiality

Subjects will be identified in the electronic CRF (eCRF) and any other document transmitted to the sponsor by the principal investigator or clinical site staff, by a unique identification number (subject number).

Data entered into the eCRF are confidential and will only be available to the sponsor (including sponsor delegates), members of data management teams, the statistician and if requested to regulatory authorities.

The Principal Investigator at each clinical investigational site will maintain, as part of the investigator site file, a list identifying all subjects entered in the clinical investigation (Subject Identification Code and Enrolment List). This list is confidential to all others than the Principal Investigator, or designee at the site.

7. Procedures

7.1. Clinical investigation-related procedures

Before initiation of the clinical investigation, Coloplast must be provided with a signed and dated curriculum vitae from the Principal Investigator and delegated personnel from each participating site (curriculum vitae not more than two years old) to verify qualifications. Coloplast will ensure that the Principal Investigator and delegated site personnel are trained in the investigational procedures, completion of the eCRFs, procedure for reporting a device deficiency, an adverse event or serious adverse event and who to contact in case of emergency related to the investigational products.

See section 7.3: Schedule of Assessments for an overview of the clinical investigation-related procedures during the investigation.

7.2. Clinical investigation related procedures and assessments

Screening Visit (V0), week 0:

- Introduction to the investigation and review of Patient Information Sheet/Informed Consent Form
- Distribution of Patient Information Sheet/Informed Consent Form
- Review of Inclusion- and exclusion criteria
- Scheduling Baseline Visit (V1) within 3 days unless performed the same day as Screening Visit (V0)

Baseline Visit (V1), week 0:

- Introduction to the investigation reviewed and confirmed
- Checking and verification of Inclusion- and exclusion criteria
- Signing of Informed Consent Form
- · Enrolment in the investigation and allocation of subject number
- Collect Baseline information:
 - o Age (years) at time of enrolment
 - o Height (cm)
 - Weight (kg)
 - o Gender (male/female)
 - o Smoking (yes/no)
 - o Alcohol (units/week)
 - Comorbidities affecting wound healing (diabetes, venous insufficiency, peripheral arterial disease, cardiopulmonary conditions, immune deficiencies, dementia or other as deemed relevant by investigator)
 - o Wound type; venous leg ulcer or diabetic foot ulcer
 - Duration of wound (date of onset)
 - o Wound treatment at time of inclusion
 - Wound size (measured by photo uploaded to a digital photo-planimetry software system)
 - Wound depth (mm)
 - For Venous Leg Ulcers: compression therapy –bandage, compression sock, other (yes/no)
 - For Diabetic Foot Ulcers: offloading (bed rest, wheelchair, crutch-assisted gait, total contact casts, felted foam, half shoes, therapeutic shoes, removable cast walkers, other).
 - o Record concomitant medication.
- · Cleansing of wound according to standard of care
- Debridement (yes/no)
- Photo of wound and upload to a digital photo-planimetry software system
- Wound assessment based on the Coloplast Wound Assessment Form (Appendix 7)
- Rave Randomization
- Dressing application according to randomization and record of dressing size used
- Additional relevant wound care products (e.g., barrier cream)
- Quality of Life assessment (Appendix 8)
- Instruction to the subject (including sheet for dressing changes between scheduled visits)
- Review potential AE/ADE/SAE/SADE/device deficiencies/Protocol Deviations
- Scheduling Visit 2 in Week 1, 7 days (-2 days) after Visit 1
- Complete eCRF
- Perform device accountability

Site visit (V2), Week 1:

- Number of dressing changes since last scheduled visit and device accountability
- Cleansing of wound according to standard of care
- Debridement (yes/no)
- Photo of wound and upload to a digital photo-planimetry software system
- For patients treated with Biatain® Silicone: photo of the dressing next to the wound bed must also be taken to assess conformability with wound bed and uploaded to a digital photo-planimetry software system
- Wound depth (mm)
- Wound assessment based on the Coloplast Wound Assessment Form (Appendix 7)
- Status of wound
- Wound healed (yes/no) if yes, the following assessments do not require completion: cleansing
 of wound, debridement, wound depth, wound assessment based on the Coloplast Wound Assessment Form, dressing application according to randomization, additional relevant wound
 care products and changes in wound dressing
- Dressing application according to randomization and recording of dressing size
- Additional relevant wound care products (e.g., barrier cream)
- Record any changes in wound dressing and specify reason and product(s)
- Record any changes in concomitant medication
- Review potential AE/ADE/SAE/SADE/device deficiencies/Protocol Deviations
- Scheduling next Study visit in the following week.
- Visit 3 must be 14 days after Visit 1 (-2 days)
- Complete eCRF

Site visit (V3), Week 2:

- Number of dressing changes since last scheduled visit and device accountability
- Cleansing of wound according to standard of care
- Debridement (yes/no)
- Conformability assessment on a 5-point Liker scale
- Photo of wound and upload in a digital photo-planimetry software system
- For patients treated with Biatain® Silicone: photo of the dressing next to the wound bed must also be taken to assess conformability with wound bed and uploaded to a digital photo-planimetry software system
- Wound depth (mm)
- Wound assessment based on the Coloplast Wound Assessment Form (Appendix 7)
- Status of wound
- Wound healed (yes/no) if yes, the following assessments do not require completion: cleansing
 of wound, debridement, wound depth, wound assessment based on the Coloplast Wound Assessment Form, dressing application according to randomization, additional relevant wound
 care products and changes in wound dressing
- Dressing application according to randomization and recording of dressing size
- Additional relevant wound care products (e.g., barrier cream)

- Record any changes in wound dressing and specify reason and product(s)
- Record any changes in concomitant medication
- Review potential AE/ADE/SAE/SADE/device deficiencies/Protocol Deviations
- Scheduling next Study visit in the following week.
- Visit 4 must be 21 days after Visit 1 (-2 days)
- Complete eCRF

[figure not shown]
Site visit (V4), Week 3:

[figure not shown]
- Number of dressing changes since last scheduled visit and device accountability
- Cleansing of wound according to standard of care
- Debridement (yes/no)
- Photo of wound and upload to a digital photo-planimetry software system
- For patients treated with Biatain® Silicone: photo of the dressing next to the wound bed must also be taken to assess conformability with wound bed and uploaded to a digital photo-planimetry software system
- Wound depth (mm)
- Wound assessment based on the Coloplast Wound Assessment Form (Appendix 7)
- Status of wound
- Wound healed (yes/no) if yes, the following assessments do not require completion: cleansing
 of wound, debridement, wound depth, wound assessment based on the Coloplast Wound Assessment Form, dressing application according to randomization, additional relevant wound
 care products and changes in wound dressing
- Dressing application according to randomization and recording of dressing size
- Additional relevant wound care products (e.g., barrier cream)
- Record any changes in wound dressing and specify reason and product(s)
- Record any changes in concomitant medication
- Review potential AE/ADE/SAE/SADE/device deficiencies/Protocol Deviations
- Scheduling next Study visit in the following week.
- Visit 5 must be 28 days after Visit 1 (- 2 days)
- Complete eCRF

Termination Visit (V5), Week 4:

- Number of dressing changes since last scheduled visit and device accountability
- Cleansing of wound according to standard of care
- Debridement (yes/no)
- Conformability assessment on a 5-point Liker scale
- Photo of wound and upload to a digital photo-planimetry software system.
- For patients treated with Biatain® Silicone: photo of the dressing next to the wound bed must also be taken to assess conformability with wound bed and uploaded to a digital photo-planimetry software system

- Wound depth (mm)
- Wound assessment based on the Coloplast Wound Assessment Form (Appendix 7)
- Status of wound
- Wound healed (yes/no) if yes, the following assessments do not require completion: Cleansing
 of wound, debridement, wound depth, wound assessment based on the Coloplast Wound Assessment Form, dressing application according to randomization, additional relevant wound
 care products and changes in wound dressing
- Additional relevant wound care products (e.g., barrier cream)
- Record any changes in wound dressing and specify reason and product(s)
- Record any changes in concomitant medication
- Review potential AE/ADE/SAE/SADE/device deficiencies/Protocol Deviations
- Quality of Life assessment (Appendix 8)
- Handover to routine care
- Complete eCRF

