5.9. Blinding

No blinding will be used in this investigation, as it is not possible to blind the products due to visible differences. The trial statistician will be blinded until database lock to ensure decisions related to data before database lock do not affect the final results.

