Quality of Life assessment	Subject		х				х	
Dressing application according to randomization	Investigator or delegate		х	х	х	х		Х
Additional relevant wound care products (e.g., barrier cream)	Investigator or delegate		х	х	х	х	х	
Record any changes in wound dressing and specify reason and product(s)	Investigator or delegate			х	х	х	х	x
Record any changes in concomitant medication				х	х	Х	х	х

	PER- FORMED BY	SCREEN- ING VISIT	BASELINE VISIT	VISIT 2	VISIT 3	VISIT 4	TERMI- NATION VISIT	UNS VISIT
			Ī					
Instruction to the subject (including sheet for dressing changes between scheduled visits)	Investigator or delegate		x					
Complete eCRF	Investigator or delegate		х	х	х	×	х	х
Handover to routine care	Investigator or delegate						×	
Perform device accountability	Investigator or delegate		X	×	×	х	х	
Schedule Baseline Visit 1	Investigator or delegate	x						
Schedule Visit 2	Investigator or delegate		x					
Schedule Visit 3	Investigator or delegate			×				
Schedule Visit 4	Investigator or delegate				x			
Schedule Termination Visit V5	Investigator or delegate					х		

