Analysis of the primary endpoint:

The percent wound area reduction (WAR) will be analyzed by an analysis of variance with treatment and wound type (VLU and DFU) as fixed effects and wound area at baseline as covariate.

The mean WAR for each treatment group will be estimated together with the 95% confidence interval. Further, the difference in mean including a 95% confidence interval between the 2 treatments will be estimated.

Analysis of the secondary endpoint:

The secondary endpoint, total cost, will be calculated as the number of products used during the investigational period multiplied by the unit price of the product. Unit price will be extracted from Drug Tarif on the date of Last Patient Out.

This secondary endpoint will be analyzed by comparing the mean cost in the two groups assuming the cost data to be normally distributed. It will be tested on a 2-sided 5% test level if the difference in mean between the two treatments is zero. Further, the mean cost for each treatment will be estimated together with a 95% confidence interval.

Analysis of exploratory endpoints:

Percentage wound depth reduction will be analyzed by the same model as described for the primary endpoint but with wound depth at baseline as covariate.

Similarly, the two endpoints related to EQ-5D-5L (the index score and the VAS score) will be analyzed by an analysis of variance with treatment as a fixed effect and the baseline measure as covariate.

The two endpoints; responder defined as a subject reaching ≥ 30% wound area reduction within the 4-week investigation period (Yes/No) and wound healed during the investigation period (Yes/No) will be analyzed by a logistic regression model with treatment and wound type (VLU or DFU) as fixed effects and wound area at baseline as covariate.

Analysis of safety endpoints:

Adverse events will be listed and summarized, if relevant. Device deficiencies and concomitant medication will be listed.

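### The visit list places the baseline EQ-5D-5L after randomisation and dressing application, and nothing requires it before allocation is known, so the covariate in the two EQ-5D-5L analyses could carry an allocation effect

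*Combined protocol and SAP*

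**What the plan says.** Section 7.2 gives the only itemised list of V1 procedures. After consent, enrolment and baseline information come cleansing, debridement, the wound photo and the wound assessment. The list then continues with "Rave Randomization", followed by "Dressing application according to randomization and record of dressing size used", additional wound care products, and only then "Quality of Life assessment (Appendix 8").

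Table 4 in Section 7.3 ticks the row "Quality of Life assessment" at V1 and V5, without a time within the visit. Appendix 9 likewise gives only the visits. Section 11.1 says that the questionnaires are handed out and completed on paper, again without a time.

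On blinding, Section 5.9 states: "No blinding will be used in this investigation, as it is not possible to blind the products due to visible differences". For the EQ-5D-5L index and VAS, Section 10.1 plans "an analysis of variance with treatment as a fixed effect and the baseline measure as covariate".

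**The concern.** A covariate used to adjust a treatment comparison should be one that treatment cannot have influenced. A site that works down the V1 list as printed would hand the questionnaire to a subject who knows the allocation and is already wearing either one dressing or a filler plus a dressing. The form in Appendix 8 asks about health on the day, including pain or discomfort, anxiety or depression, and an overall health scale, so answers could respond to events earlier in the same visit.

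If they did, the adjusted analysis would subtract part of a treatment effect, or produce an apparent one in the opposite direction. Recruiting more subjects would not remove this. Sites could also differ in when they give the form, and no section asks for the time of completion, so the order could not be checked afterwards. The EQ-5D-5L is the only subject-assessed endpoint in Appendix 9, and Section 5.5 describes quality of life as an important outcome for patients.

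**Working it through.** **Order of procedures.** The plan contains no figure to reproduce on this point, so the first step is to compare the places that bear on timing.

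- Section 7.2, V1 list: the questionnaire comes third after randomisation, following dressing application and additional products.
- Table 4: the quality-of-life row is above dressing application but below randomisation.
- Appendix 9 and Section 11.1: no order within the visit.

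None of these places the questionnaire before randomisation, and none requires it there.

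**Size of the bias.** With treatment and the V1 score in the model, the adjusted difference is

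(mean V5, test − mean V5, control) − b × (mean V1, test − mean V1, control),

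where b is the within-arm slope of V5 on V1. When V1 is taken before randomisation, the second bracket has expectation zero. If allocation shifts the recorded V1 score by d between arms, its expectation is d, and the estimate moves by −b × d. Two cases:

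- The shift fades before V5 and there is no true V5 difference: the expected estimate is 0 − b × d, an apparent effect of opposite sign.
- The shift persists to V5 in full: the true difference is d and the expected estimate is d − b × d = (1 − b) × d, so a share b of the effect is lost.

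**Illustration.** The documents give no EQ-5D-5L standard deviation, no V1–V5 correlation and no allocation effect. The inputs below are assumptions, in SD units, except for the 40 completers per arm from Section 10.2. The first case was simulated with 4,000 runs per row, with V1 and V5 both of SD 1 so that b equals the correlation.

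| b | d | −b × d | Mean simulated estimate | Rejection at nominal 5% |
|---|---|---|---|---|
| 0.5 | 0 | 0 | 0.006 | 5.3% |
| 0.5 | 0.1 | −0.05 | −0.052 | 5.5% |
| 0.5 | 0.2 | −0.10 | −0.098 | 8.1% |
| 0.5 | 0.3 | −0.15 | −0.145 | 10.8% |
| 0.7 | 0 | 0 | 0.002 | 5.4% |
| 0.7 | 0.1 | −0.07 | −0.070 | 6.9% |
| 0.7 | 0.2 | −0.14 | −0.144 | 14.0% |
| 0.7 | 0.3 | −0.21 | −0.212 | 25.2% |

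The simulation error near 5% is about √(0.05 × 0.95 / 4,000) = 0.34 percentage points, so the 5.5% in the second row cannot be told apart from no effect.

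On the VAS, again by assumption, d from 0 to 5 points and b from 0.5 to 0.8 give a bias from 0 to 0.8 × 5 = 4.0 points in size; d = 2 with b = 0.5 gives 1.0 point.

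**The case against.** The strongest reply is that the bullets are not declared a mandatory sequence and in places cannot be one. In the V2 to V5 lists, the healed-wound item that waives cleansing, debridement and depth comes after those items. At V1, wound size by photo appears under baseline information, above the photo itself. Table 4 orders its rows differently, with randomisation above the collection of baseline information. A reader might infer from the V1 list that the form is in fact completed after allocation at every site. The documents do not support that: they show where it is listed and that no earlier time is required. This part of the reply stands. It does not close the gap, because no section supplies the missing requirement and a site following the list as printed would take the score late.

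A reader might also infer that randomisation no longer protects the EQ-5D-5L comparison at all. That goes too far. Only the baseline-adjusted estimate is exposed to this bias; a comparison of V5 scores without the covariate remains a randomised one.

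The reply is also right that the consequences are limited. Section 5.4 classes both EQ-5D-5L scores as exploratory, Section 10.1 calls the study exploratory, and the criterion in Section 10.4 uses wound area and cost only. Any shift would have to arise within one visit, between two CE-marked regimens, on a general health instrument, so it may be small or absent.

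**Conclusion.** The point holds as a gap in the timing of a covariate. The V1 list places the baseline EQ-5D-5L after randomisation and dressing application, nothing requires it earlier, and the open-label design makes an allocation effect on that score possible. If there is one, the bias in the adjusted V5 difference is −b × d. Its size is unknown: the illustrated 0.05 to 0.21 SD, and the 0 to 4 VAS points, rest wholly on assumed values of d and b. Two exploratory analyses are exposed. Wound area, cost and the pass/fail criterion are not. The change is worth making because it removes this source of bias at little cost, not because a bias has been shown.

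**What to change.** In Section 7.2, Baseline Visit (V1), move the quality-of-life item to after the signing of consent and before "Rave Randomization". In Table 4, state that the V1 questionnaire is completed before randomisation.

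It need not precede cleansing and debridement: both are listed before randomisation, and completion before randomisation is enough to remove this bias. No change to V5 is needed.

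The cost is a small amendment under Section 12, with any ethics committee notification it requires, and site training. The front page gives a last submission date of March 15, 2023, while Section 5.10 gives January 2023 as the approximate date of first enrolment, so recruitment may already have begun. If so, record which subjects completed the form before the change and which after it, so that the two baseline timings can be told apart in the analysis.

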7.2.2. Dressing changes between site visits

If the wound requires frequent dressing changes (more than once scheduled visit per week), unscheduled visits at the site can be scheduled for dressing changes.

The dressing change can also take place at the subjects home by the subject or by a homecare nurse. The subject will be provided with the additional study products to which he/she is allocated at each visit to use at home in case of additional dressing changes in between visits. An information sheet for the homecare nurse will be distributed to the subjects to be shared with the homecare nurse, providing information about the study and the study treatment to ensure that the protocol is followed between scheduled visits.

In the event of a completed dressing change between the weekly scheduled visits, it must be documented at the next scheduled weekly visit in the eCRF to capture the total number of dressings since last scheduled visit. The subject will be instructed to complete a sheet for dressing changes between the scheduled weekly site visits capturing the dressing change and date of the event.

No clinical investigation-related wound assessments are conducted during the unscheduled visits and/or dressing changes at the subjects home. Cleansing of wound must be done according to standard of care and debridement, if needed. The dressing applications between weekly scheduled visits must be according to randomization.

The total number of dressings, the sizes of the dressings used and frequency of dressing changes per subject is part of the cost-effectiveness analysis.

7.3. Schedule of clinical related procedures and assessments

Table 4: Chart showing the connection between visits and assessments.

	PER- FORMED BY	SCREEN- ING VISIT	BASELINE VISIT	VISIT 2	VISIT 3	VISIT 4	TERMI- NATION VISIT	UNS VISIT
VISIT	g.	V0	V1	V2	V3	V4	V 5	
WEEK		WEEK 0	WEEK 0	WEEK 1	WEEK 2	WEEK 3	WEEK 4	
VISIT WINDOW			0-3 days after V0	-2 days 7 DAYS	-2 days 14 DAYS	-2 days 21 DAYS	-2 days 28 DAYS	
GENERAL								
Introduction to the investiga- tion and review of Patient In- formation Sheet/Informed Con- sent Form	Investigator or delegate	x	х					
Check and verification of in- and exclusion criteria	Investigator or delegate		х					
Review of in- and exclusion criteria		х						
Informed Consent Signed	Investigator and Subject		х					
Enrollment in the investigation allocation of subject number	Investigator or delegate		х					
Randomization	Investigator or delegate		x					
Collect Baseline information	Investigator or delegate		x					
Record concomitant medication	Investigator or delegate		x					
Review of AE/ADE/SAE/SADE/device deficiencies/Protocol Devia- tions	Investigator or delegate		X	x	х	х	x	x
QUESTIONNAIRES AND ASSESSMENTS								
Number of dressing changes since last visit	Investigator or delegate			x	x	×	x	
Cleansing of wound according to standard of care	Investigator or delegate		x	x	x	×	х	х
Debridement yes/no	Investigator or delegate		Х	х	х	х	х	

	PER- FORMED BY	SCREEN- ING VISIT	BASELINE VISIT	VISIT 2	VISIT 3	VISIT 4	TERMI- NATION VISIT	UNS VISIT
Photo of wound and upload to a digital photo-planimetry soft- ware system	Investigator or delegate		x	×	×	×	x	
Wound assessment based on the Coloplast Wound Assess- ment Form	Investigator or delegate		х	х	х	х	х	
Wound depth (mm)	Investigator or delegate		х	х	х	х	×	
Status of wound	Investigator or delegate			х	х	х	х	
For patients treated with Bi- atain® Silicone: photo of the dressing next to the wound bed must also be conducted to assess conformability with wound bed and upload to a digital photo-planimetry soft- ware system	Investigator or delegate			x	x	x	x	
Wound healed (yes/no) if yes, the following assessments do not require completion: Cleansing of wound, debridement, wound depth, wound assessment based on the Coloplast Wound Assessment Form, dressing application according to randomization, additional relevant wound care products and changes in wound dressing	Investigator or delegate			Х	X	X	X	х
Conformability assessment	Investigator or delegate				х		х	
Quality of Life assessment	Subject		х				х	
Dressing application according to randomization	Investigator or delegate		х	х	х	х		Х
Additional relevant wound care products (e.g., barrier cream)	Investigator or delegate		х	х	х	х	х	
Record any changes in wound dressing and specify reason and product(s)	Investigator or delegate			х	х	х	х	x
Record any changes in concomitant medication				х	х	Х	х	х

	PER- FORMED BY	SCREEN- ING VISIT	BASELINE VISIT	VISIT 2	VISIT 3	VISIT 4	TERMI- NATION VISIT	UNS VISIT
			Ī					
Instruction to the subject (including sheet for dressing changes between scheduled visits)	Investigator or delegate		x					
Complete eCRF	Investigator or delegate		х	х	х	×	х	х
Handover to routine care	Investigator or delegate						×	
Perform device accountability	Investigator or delegate		X	×	×	х	х	
Schedule Baseline Visit 1	Investigator or delegate	x						
Schedule Visit 2	Investigator or delegate		x					
Schedule Visit 3	Investigator or delegate			×				
Schedule Visit 4	Investigator or delegate				x			
Schedule Termination Visit V5	Investigator or delegate					х		

